#### 5.5.1.1. Adjustments for Covariates

Unless otherwise specified (e.g. PGI-I analysis), the MMRM models will include the fixed, categorical effects of treatment, month, and treatment-by-month interaction, as well as the continuous, fixed covariates of baseline value and baseline-by-month interaction. The baseline value and baseline-by-month interaction are included to account for the differential influence over time that the baseline value has on the post-baseline values.

Except for efficacy analyses on migraine headache days, the baseline number of MHD ( $<8$ ,  $\geq 8$ ) is added as a categorical covariate for the MMRM model specified above.

When an ANCOVA model is used to analyze a continuous efficacy or safety variable at LOCF endpoint, the model will contain the main effects of treatment, and appropriate baseline value (baseline of the response variable) as a covariate.

When ANCOVA is used for the primary endpoint, Month 1 to Month 6 values are imputed first using for any missing data by LOCF. Then the change from baseline for overall period (Month 1 to Month 6) is calculated as the average of change from baseline to Month 1, change from baseline to Month 2, ..., change from baseline to Month 6. The statistical model contains treatment effect and baseline MHD value (continuous). Statistical tests for treatment effect (LY120 vs. placebo, or LY240 vs. placebo) are based on the main effect of the treatment.

The GLIMMIX models for the repeated binary outcomes will include the fixed, categorical effects of treatment, month, and treatment-by-month interaction, as well as the continuous, fixed covariate of baseline value. In addition, the baseline number of MHD (<8, >=8) is added as a categorical covariate except for categorical analysis of response rate (such as 20% response rate) derived from migraine headache days where the continuous value of baseline migraine headache days will be used as covariate.

For example, consider MHD 50% responder analysis. "The continuous, fixed covariate of baseline value" equals to (continuous) MHD at baseline (Month 0) because MHD 50% responder is derived from (continuous) MHD at each month. The baseline value-by-month interaction will be excluded from the model in order to increase the likelihood of convergence.

For example, MIDAS 50% responder at month 6 analysis, the baseline number of MHD (<8, >=8) is added as a categorical covariate for the GLIMMIX model specified above.

For example, PGI-S responder analysis (based on average of month 4, month 5, and month 6), the model includes treatment, month, treat\*month, baseline (PGI-S) and the baseline number of MHD (<8, >=8).

When a logistic regression is used to analyze a binary variable, the model will include the main effect of treatment, and appropriate baseline value as a covariate.

- For MSQ Role Function-Restrictive responder (change from baseline >=25) analysis, the baseline number of MHD (<8, >=8) and baseline score of MSQ Role Function-restrictive are added as covariates.
- For positive response analysis in PSMQ-M, the baseline number of MHD (<8, >=8) is added as a categorical covariate
- For maintenance of 50% response analysis for the last 3 months or 6 months, the baseline MHD (continuous) is added as a covariate.

For time to event analysis of 50% response (such as Time to first 50% response in double-blind treatment phase and Time to first loss of 50% response in post-treatment phase), stratified log

rank test will be used with the baseline number of MHD category ( $<8$  vs  $\geq 8$ ) as the stratification factor and the treatment as the covariate.

#### 5.5.1.2. Handling of Dropouts or Missing Data

Two statistical approaches to handling missing data will be used as appropriate: repeated measures analyses and ANCOVA.

For the repeated measures analyses, the model parameters are simultaneously estimated using restricted likelihood estimation incorporating all of the observed data. Estimates have been shown to be unbiased when the missing data are MAR.

For ANCOVA model, response values at each visit will be imputed by LOCF first, then the average of 6 months (double blind period) for the response value will be derived. (Section 5.5.1.1).

Please refer to Section 5.4.1 for general approach to handling missing diary data for derivation of the number of migraine headache days and other efficacy measures (some exceptions: migraine attacks) derived from ePRO data.

#### Approaches to Handling Missing Diary Data for the Derivation of Migraine Attack

For the analysis of migraine attack, the LOCF method will be used to impute the missing ePRO diary days. In other words, if the patient was migraine headache free on the day before the missing ePRO diary day, this would be carried forward as no migraine headache day until the actual next non-missing call day. On the other hand, if the day before the missing diary day is a migraine headache day, then it would be carried forward as migraine headache day until the next non-missing diary day. The imputation will be carried out for all the missing diary days between the first non-missing to the last day during that period.

If the compliance rate for a monthly interval is  $\leq 50\%$ , the number of migraine attacks during that month will be considered missing. Please refer to Section 5.4.1 and Section 5.5.7 for compliance rate calculation.

#### 5.5.1.3. Analysis Populations

Analysis populations are defined below:

**All Patients:** All patients who signs informed consent.

**All Randomized Patients (ARP):** All patients who are randomized at Visit 3.

**Intent-to-Treat (ITT) Population:** All patients who are randomized at Visit 3 and received at least one dose of the study drug. Patients in the ITT population will be analyzed according to the treatment that they were randomized to. Unless otherwise specified, the ITT population will be the primary population on which statistical analysis will be performed.

**Post-treatment Population:** All patients who entered the post-treatment phase (Study Period IV) as indicated by entering any post-treatment visit. Patients in the post-treatment population will be analyzed according to the treatment that they were randomized to at Visit 3. Post-treatment Population is a subset of ARP.

**ADA Follow-up Cohort:** All patients who are post-treatment population and have both baseline and at least one postbaseline ADA assessment during SP IV.

**Per Protocol Set (PPS):** Intent-to-treat population who has no important protocol deviation which impacts efficacy analysis. Details will be specified in Section 5.5.3.

**Safety Population:** This is the same as the ITT population except the assigned arm definition. It is determined by modal treatment the patient received during the double-blind treatment period (up to the injection visits if they discontinue early). For determining modal treatment, do not consider the loading dose visit for patients assigned to an LY120-mg treatment group, but do consider it for patients assigned to the placebo and LY240-mg treatment groups. If there are 2 or more modes, then add the loading dose visit and recalculate the mode. If there is still a tie, the highest dose of the modes is to be used.

**Example 1:** Suppose a patient, randomized as LY120-mg treatment group, discontinues at Visit 5 (Month 1) who has LY 240-mg loading dose at Visit 3 (Month 0) and no dose at Visit 5 (Month 1). It implies mode is not unique, because Visit 3 dosing is omitted. Its mode is 0mg, 120mg, 240mg (counted as zero at each dose). Then the patient is assigned to LY240-mg arm group (the highest dose) as safety population.

**Example 2:** Suppose a patient, randomized as LY120-mg treatment group, discontinues at Visit 6 (Month 2) who has LY 240-mg loading dose at Visit 3 (Month 0), LY 120-mg dose at Visit 5 (Month 1) and no dose at Visit 6. Then the patient is assigned to LY120-mg arm group as safety population.

PPS is used for a sensitivity analysis on the primary efficacy analysis.

Unless otherwise specified, safety population is used for safety analysis and exposure.

Unless otherwise specified, statistical analysis for efficacy will be carried out for 6 months treatment phase (Study Period III), 4 months post-treatment phase (Study Period IV), and/or 6 months treatment and 4 months post-treatment phase combined (Study Period III /IV) based on following population:

- For the analyses in Study Period III, the **ITT population** will be used.
- For the analyses in Study Period III/IV, the **ITT population** will be used.
- For the analyses in Study Period IV, the **post-treatment population** will be used.

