**5.5.1.4. Baseline and Post-Baseline Definition**

Table CGAN. 5.4 describes the rules for determining the patient population and baseline and post-baseline observations for each study phase and type of analysis. When “last of Visit x-x” is used in the table, the last nonmissing observation obtained in the visit interval will be used.

Table CGAN. 5.4 Patient Population with Baseline and Post-Baseline Definitions by Study Period and Type of Analysis

Study Period / Analysis	Patient Population	Baseline Observation	Post-baseline Observation(s)
Study Period III			
Primary / Secondary / Exploratory efficacy analyses (Repeated Measures)	ITT Population with a baseline and at least one post-baseline observation	Visit 3	All Visits 3.01–12
Primary efficacy analyses (Repeated Measures)	PPS with a baseline and at least one post-baseline observation	Visit 3	All Visits 3.01–12
Primary / Secondary / Exploratory efficacy analyses at LOCF endpoint or for average of observed monthly values	ITT Population with a baseline and at least one post-baseline observation	Visit 3	Visit 3.01-12
Quality of Life analyses (Repeated Measures)	ITT Population with a baseline and at least one post-baseline observation	Visit 3	All Visits 3.01–12
Quality of Life analyses at LOCF endpoint or for average of observed monthly values	ITT Population with a baseline and at least one post-baseline observation	Visit 3	Visit 3.01-12
TEAEs	Safety Population	All Visits 1–3. Pre-existing condition that is still ongoing at Visit 1 should be evaluated as baseline values.	All Visits 3.01–12
Serious Adverse Events, Discontinuations due to Adverse Events	Safety Population	NA	All Visits 3.01–12
C-SSRS categorical analyses	Safety population with a baseline and at least one post-baseline C-SSRS assessment	Recent History: All Visits 1–3 excluding lifetime a All Prior History: Visits 1 – 3 including lifetime a	All Visits 3.01–12
Treatment emergent abnormal laboratory values	Safety Population with normal laboratory values at all nonmissing baseline visits (with respect to direction being analyzed) and who have at least one post-baseline observation	All Visits 1–3	All Visits 3.01–12
Treatment emergent immunogenicity	Safety Population, ADA follow-up cohort (See Section 5.5.12.1.6)	Visit 3	All Visits 3.01–12
Treatment emergent changes in vital signs, weight,	Safety Population with a baseline and at least one	Low:	Low:

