Study Period / Analysis	Patient Population	Baseline Observation	Post-baseline Observation(s)
and ECGs	post-baseline observation	Minimum value from Visits 1–3  High: Maximum value from Visits 1–3	Minimum value from Visits 3.01–12  High: Maximum value from Visits 3.01–12
Continuous safety analyses (Repeated Measures)	Safety Population with a baseline and at least one post-baseline observation	Last of Visits 1–3	Scheduled visits: 3 < Visits <= 12
Continuous safety analyses – change from baseline to LOCF endpoint (ANCOVA)	Safety Population with a baseline and at least one post-baseline observation	Last of Visits 1–3	Last scheduled visit: 3 < Visit <= 12
Study Period III and IV combined			
Primary / Key Secondary efficacy analyses	ITT Population with a baseline and at least one post-baseline observation	Visit 3	All Visits 3.01–14
Quality of Life analyses	ITT Population with a baseline and at least one post-baseline observation	Visit 3	All Visits 3.01–14
Continuous safety analyses (Repeated Measures)	Safety Population with a baseline and at least one post-baseline observation	Last of Visits 1–3	All Visits 3.01–14
Treatment emergent immunogenicity	Safety Population, ADA follow-up cohort (See Section 5.5.12.1.6)	Visit 3	All Visits 3.01–14
Study Period IV			
Continuous safety analyses – change from baseline to LOCF endpoint (ANCOVA)	Post-treatment Population with a baseline and at least one post-baseline observation	Last of Visits 1–12	Last Visit: 12.01–14
FEAEs	Post-treatment Population	All Visits 1–12. Pre-existing condition that is still ongoing at Visit 1 should be evaluated as baseline values.	All Visits 12.01–14
Serious Adverse Events, Discontinuations due to Adverse Events	Post-treatment Population	NA	All Visits 12.01–14
Follow-up emergent abnormal laboratory values	Post-treatment Population with normal laboratory values at all nonmissing baseline visits (with	All Visits 1–12	All Visits 12.01–14

Study Period / Analysis	Patient Population	Baseline Observation	Post-baseline Observation(s)
	respect to direction being analyzed) and who have at least one post-baseline observation		
Follow-up emergent changes in vital signs, weight and ECGs	Post-treatment Population with a baseline and at least one post-baseline observation	Low: Minimum value from Visits 1–12  High: Maximum value from Visits 1–12	Low: Minimum value from Visits 12.01–14  High: Maximum value from Visits 12.01–14

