C-SSRS categorical analyses	Post-treatment Population with a baseline and at least one post-baseline C-SSRS assessment	Recent History: All Visits 1–12 excluding lifetime a All Prior History: Visits 1 – 12 including lifetime a	All Visits 12.01–14

Abbreviations: ADA = Anti-Drug Antibody; ANCOVA = analysis of covariance; C-SSRS = Columbia Suicide Severity Rating Scale; FEAE = follow-up emergent adverse event; ITT = intent-to-treat; LOCF = last observation carried forward; PPS = per protocol set; TEAE = treatment emergent adverse event.  
Note: Visit 3.01 indicates the first unscheduled visit occurring after Visit 3 and prior to Visit 4. Visit 12.01 indicates the first unscheduled visit occurring after Visit 12 and prior to Visit 13. For efficacy and quality of life measures without unscheduled visits data point, Visit 3.01 indicates scheduled collection visits after visit 3.

a Lifetime is captured in the C-SSRS visit 1 CRF.

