#### **5.5.12.1. Categorical Safety Variables**

Unless specified otherwise, the categorical safety analyses will include both scheduled and unscheduled visits. Unless otherwise specified, categorical safety analyses will only be conducted for Study Period III and Study Period IV separately.

Comparisons between treatment groups for all categorical safety measures will be made using the Fisher's exact test for Study Period III with the safety population.

Descriptive statistics only will be presented for the treatment groups in Study Period IV with the post-treatment population.

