##### **5.5.12.1.1. Adverse Events**

Treatment-emergent adverse events are defined as the reported AEs that first occurred or worsened during the post-baseline phase compared with the baseline phase. Pre-existing condition that is still ongoing at Visit 1 should be evaluated as baseline values. For each TEAE, the severity level of the event (mild, moderate, or severe) will be determined by patient or physician opinion. The MedDRA Lowest Level Term (LLT) will be used in the treatment emergent computation. For each LLT, the maximum severity at baseline will be used as the baseline severity. If the maximum severity during post-baseline is greater than the maximum baseline severity, the event is considered to be treatment emergent for the specific post-baseline period. For each patient and TEAE, the maximum severity for the MedDRA level being displayed (PT, High Level Term, or SOC) is the maximum post-baseline severity observed from all associated LLTs mapping to that MedDRA level.

Follow-up emergent adverse events (post-treatment emergent adverse events) are defined similarly. It is an event that first occurred or worsened during the follow-up period (Study Period IV) when compared to the baseline (SP I, SP II, and SP III). Pre-existing condition that is still ongoing at Visit 1 should be evaluated as baseline values.

For events that are gender-specific, the denominator and computation of the percentage will include only patients from the specific gender.

Following summary will be created:

- Overview of AE (SP III)
- TEAEs (SP III)
  - By PT by decreasing frequency
  - By PT by decreasing frequency with an incidence in either galcanezumab treatment group  $\geq 1.5\%$  and greater than placebo.
  - By SOC/PT
  - By maximum severity/PT
- FEAEs (SP IV)
  - By PT by decreasing frequency
  - By SOC/PT
  - By maximum severity/PT
- TEAEs by considered to be related to investigational product by investigator (SP III)
- Treatment Emergent Adverse Events that started on Treatment phase and Continuing in Post-Treatment Phase (SP III, SP IV combined)
- SAEs (SP III, SP IV separately)
- AEs leading to discontinuation (SP III, SP IV separately)

Listing of Subjects with TEAE or FEAE (SP III, SP IV combined) will be created.

Listing of Adverse Events Leading to Discontinuation and Serious Adverse Events (SP I, SP II, SP III, SP IV combined) will be created.

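### A new SAE or death after Visit 12/ET in a non-rollover patient with no post-treatment visit record is counted in neither period's safety table, and the two periods group patients into arms differently

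*SAP*

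**What the plan says.** **Membership and arm.** SAP 5.5.1.3 defines the Post-treatment Population as "All patients who entered the post-treatment phase (Study Period IV) as indicated by entering any post-treatment visit", and Protocol Table CGAN.10.1 has the same rule. The SAP adds "Post-treatment Population is a subset of ARP" and keeps these patients in the arm to which they were randomised. The Safety Population, in the same SAP section, contains the ITT patients but groups them by the modal treatment received in the double-blind period.

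**Windows.** SAP Table CGAN. 5.4 gives for Study Period III "Serious Adverse Events, Discontinuations due to Adverse Events Safety Population NA All Visits 3.01–12" and for Study Period IV "Serious Adverse Events, Discontinuations due to Adverse Events Post-treatment Population NA All Visits 12.01–14". Follow-up-emergent AEs use the same population and window as the second row. SAP 5.5.12.1 confirms: "Descriptive statistics only will be presented for the treatment groups in Study Period IV with the post-treatment population". A note to Table CGAN. 5.4 says "Visit 12.01 indicates the first unscheduled visit occurring after Visit 12 and prior to Visit 13".

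**Outputs.** SAP 5.5.12.1.1 plans "SAEs (SP III, SP IV separately", and also "Listing of Adverse Events Leading to Discontinuation and Serious Adverse Events (SP I, SP II, SP III, SP IV combined) will be created".

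**Entry into Study Period IV.** Under Protocol Section 8, patients who stop during Study Period III pass straight into Study Period IV. Under Protocol 5.1, completers who do not join CGAP also go there. Neither section makes a later visit a condition. The Schedule of Activities puts the first scheduled visit, Visit 13, at 60 ± 5 days after Visit 12.

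**The concern.** Protocol 5.4 says the follow-up phase is there to evaluate safety during wash-out. The protocol places a patient in that phase by status, but the SAP recognises the patient for safety tables only through a later visit record. A death or serious event can itself be the reason that no visit is recorded. In that case the event leaves the numerator and the patient leaves the denominator, and the preceding period's table has already closed. A listing gives no count or rate by arm.

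The arm rule is a second, separate matter. If the two periods group patients differently, a reader who sets the Study Period III and Study Period IV safety tables side by side is not comparing the same people within a column.

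**Working it through.** The main check traces one event through the populations and windows. The arithmetic only gives a scale.

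**1. Trace.** Take a dosed patient who has Visit 12/ET, does not enter CGAP, and then has a first SAE or dies before any further visit is recorded.
- Study Period III SAE table: the patient is in the Safety Population, but the window ends at Visit 12. Not counted.
- Study Period IV SAE and follow-up-emergent AE tables: the event falls in time within the follow-up phase, but the patient has no post-treatment visit and so is not in the Post-treatment Population. Not counted.
- Combined tables: the Study Period III/IV rows of Table CGAN. 5.4 cover efficacy, quality of life, continuous safety and immunogenicity. None covers SAEs. The one combined AE summary in SAP 5.5.12.1.1 takes events that began in the treatment phase and continued, so a new event is not in it.
- All-period listing of SAEs and AE discontinuations: no visit condition is stated. The event appears here.

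**2. What would bring the patient back in.** An unscheduled Visit 12.01 or a Visit 14/ET record could establish membership. The gap therefore concerns patients with no post-treatment visit record of any kind. If Visit 13 is missed, it can extend beyond the first 60 days.

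**3. Arms.** In Example 1 of SAP 5.5.1.3, a patient randomised to 120 mg receives only the 240 mg loading dose and discontinues at Visit 5. The SAP places that patient in the 240 mg arm of the Safety Population. Protocol Section 8 sends the same patient to Study Period IV, where the Post-treatment Population uses the randomised arm, 120 mg. The combined Study Period III/IV continuous safety models (SAP 5.5.12.2) use the Safety Population, so there the patient is again in the 240 mg arm.

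**4. Scale.** Inputs: 451 randomised, 15% discontinuation and 383 completers (SAP 5.2); about 240 rollovers (Protocol 7.8.1); Visits 13 and 14 at 60-day intervals, each ± 5 (Schedule of Activities).
- Completers: 451 × (1 − 0.15) = 383.35, which reproduces the plan's 383.
- Study Period IV, completers only: 383 − 240 = 143. If every early discontinuer also enters: 451 − 240 = 211.
- Interval before Visit 13: 60 of 120 days, half the phase. Patient-time: 143 × 60/365.25 = 23.5 years; 211 × 60/365.25 = 34.7 years.
- Patients with no visit record: the documents give no rate. Assuming 1% to 10%: 0.01 × 143 = 1.4, up to 0.10 × 211 = 21.1.
- Weight of one event, if rollover is proportional to randomisation (also an assumption): each galcanezumab arm has 143 × 113/451 = 36 to 211 × 113/451 = 53 patients, so one SAE is 1/36 = 2.8% to 1/53 = 1.9% of the arm.

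**The case against.** The strongest reply is that the SAP never says *entering* a visit means coming to the site. Unscheduled visits lie inside the Study Period IV window. Protocol 5.1 expects ET measurements from anyone who leaves Study Period IV, ET shares the Visit 14 column, and SAP 5.4.1 already relies on a Study Period IV disposition date. A reader might infer that membership needs attendance in person; the documents do not support that. What remains is that the SAP does not say whether an ET or disposition record made without attendance counts, and for a death that is the deciding case.

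A reader might also infer that the event goes unreported. It does not: it is in the all-period listing. SAP 5.5.2 also tabulates disposition for Study Period IV and lists discontinuers in the ITT population. What is lost is the count by arm.

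Three further inferences are not supported:
- **That Study Period IV rates are biased low.** Leaving out event-free patients raises a rate. It falls only if those left out have more events than those kept, and the documents give no such rates. These tables are also descriptive, with no tests.
- **That the registry summary has the same gap.** SAP 5.9 splits it by period but names no population.
- **That undosed patients enter because the population is nested in all randomised patients.** Dosing starts at the randomisation visit, and Study Period IV takes those who complete or stop Study Period III. No consequence is shown.

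The arm mismatch is a different issue from the counting gap and should be judged separately. None of these replies touches it.

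**Conclusion.** The concern holds in limited form. On a literal reading, a new SAE or death after Visit 12/ET in a non-rollover patient with no post-treatment visit record enters neither period's by-arm table, and no combined SAE table picks it up. The number affected is unknown and probably small. The 1 to 21 patients computed here rest on an assumed 1% to 10% without a visit record and on 143 to 211 patients in the phase. They count patients left out, not events missed. Because the arms are small, one uncounted event could still be about 2% to 3% of a galcanezumab arm. The direction of any bias is not established, and the primary analysis is unaffected.

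The arm inconsistency follows from the SAP's own example and needs no assumption, although how often it would occur is not known. Both points are worth correcting because they affect the wash-out safety tables and are cheap to close.

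**What to change.** For the Study Period IV AE, SAE and discontinuation tables, define the population by a rule that does not depend on outcome: all Safety Population patients who were alive at the end of Study Period III (Visit 12/ET) and did not roll over to CGAP, whether or not a later visit was recorded. Analyse them in the same arm as in the Study Period III safety tables. State which date closes Study Period III for a patient with no ET visit.

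Do not admit patients because they have an AE. That would bring in no-visit patients with events while leaving out those without, and so condition the denominator on the outcome. Keep the visit-based rule for laboratory, vital sign, ECG and antibody measures.

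Alternatively or in addition, plan a combined Study Period III/IV table of SAEs and deaths on the Safety Population. This closes the counting gap, but on its own it leaves the arm mismatch in the separate Study Period IV tables.

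The cost is SAP wording and one flag. The Study Period IV denominator becomes slightly larger and includes some patients with little follow-up, which a footnote should say.
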